### **8.5.2 Method of Detecting AEs and SAEs**

Care will be taken not to introduce bias when detecting AEs and/or SAEs. Open-ended and non-leading verbal questioning of the subject is the preferred method to inquire about AE occurrences.

### **8.5.3 Follow-up of AEs and SAEs**

After the initial AE/SAE report, the investigator is required to proactively follow each subject at subsequent visits/contacts. SAEs and AEs will be followed until resolution, stabilization, the event is otherwise explained, or the subject is lost to follow-up (as defined in Section 7.3). AEs not considered serious or as an AESI will be considered ongoing if they have not resolved by Week 52. Further information on follow-up procedures is given in Section 10.3, Appendix 3.

### **8.5.4 Regulatory Reporting Requirements for SAEs**

Prompt notification by the investigator to the sponsor of a SAE is essential so that legal obligations and ethical responsibilities towards the safety of subjects and the safety of a study drug under clinical investigation are met.

The sponsor has a legal responsibility to notify both the local regulatory authority and other regulatory agencies about the safety of a study drug under clinical investigation. The sponsor will comply with country-specific regulatory requirements relating to safety reporting to the

regulatory authority, Institutional Review Boards (IRB)/Independent Ethics Committees (IEC), and investigators. AEs/SAEs must be followed up and reported as appropriate for at least 8 weeks (5 terminal half lives) after the last study dose.

Investigator safety reports must be prepared for suspected unexpected serious adverse reactions (SUSAR) according to local regulatory requirements and sponsor policy and forwarded to investigators as necessary.

An investigator who receives an investigator safety report describing a SAE or other specific safety information (e.g., summary or listing of SAEs) from the sponsor will review and then file it along with the Investigator's Brochure and will notify the IRB/IEC, if appropriate according to local requirements.

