**Figure 2 – Proportion of Subjects with PASI 75/90/100 at Day 85 (Week 12) in Study EMR200574-003**

#### 4.4 End of Study Definition

The end of study participation for each subject will be after 52 weeks. The end of the overall study is defined as the date of the last subject’s last visit globally across all countries.

At the time of the last subject’s last visit, any SAEs or AESI that are unresolved will be considered ongoing.

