### **6.7 Treatment after the End of the Study**

The final dose of study drug will be administered at the Week 44 visit with the final study visit occurring at Week 52.

Subjects that discontinue study treatment during the study should complete Early Discontinuation, with visits approximately 4 weeks (28 days) and 8 weeks (56 days) after the last dose of study drug (see the SoA, Section 1.3, and Sections 7.2 and 8.1.11). Once the Early Discontinuation visits have been completed, subjects will be contacted by telephone as per the q4w study schedule.

After study completion at Week 52, or after completion of the Early Discontinuation visits, subjects should be treated as per local guidance and physician recommendation.

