## 8.0 STUDY ASSESSMENTS AND PROCEDURES

- Study procedures and their timing are summarized in the SoA (Section 1.3). Study visit dates are scheduled relative to Week 0.
- Protocol waivers or exemptions are not allowed.
- Immediate safety concerns should be discussed with the sponsor immediately upon occurrence or awareness to determine if the subject should continue or discontinue study drug.
- Adherence to the study design requirements, including those specified in the SoA (Section 1.3), is essential and required for study conduct.
- All screening evaluations must be completed and reviewed to confirm that potential subjects meet all eligibility criteria. The investigator will maintain a screening log to record details of all subjects screened and to confirm eligibility or record reasons for screening failure, as applicable.
- Patient Reported Outcomes (PROs) during any visit should be conducted before other tests, procedures, or consultations.
- IGA, BSA and PASI during any visit should be conducted after the PROs (if applicable) and before other tests, procedures and consultations. As far as possible, the same evaluator should perform the IGA, BSA and PASI at all visits for a particular subject, especially at Week 0 (randomization), Week 12, and Week 24.
- The maximum amount of blood collected from each subject over the duration of the study, including any extra assessments that may be required, will not exceed 565mL, with a maximum 50mL taken at any visit. Repeat or unscheduled samples may be taken for safety reasons or for technical issues with the samples.

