There is a visit window of  $\pm 1$  day for the Week 4 visit.

Patient reported outcomes (PRO) i.e. PHQ-8, and eC-SSRS should be performed before any other study procedures, assessments or consultations.

IGA, BSA and PASI should be conducted after the PROs and before other tests, procedures and consultations.

Study drug should be administered after completion of all other study procedures.

The following assessments will be performed and information collected:

- PHQ-8
- eC-SSRS
- IGA
- BSA
- PASI
- AEs
- Concomitant Medications
- Skin Evaluation
- Physical Examination
- Vital Signs
- Laboratory Analysis Chemistry and Haematology (Central Laboratory)
- Urine Pregnancy Test (Local) – if positive, study drug must be withheld and a Serum Pregnancy Test (Central Laboratory) performed

- Blood Sample for Immunogenicity (must be pre-dose)
- Blood Sample for Pharmacokinetics (must be pre-dose)
- Study Treatment (allocated via IRT)

#### 8.1.6 Weeks 8, 44, 52

There is a visit window of  $\pm 2$  days for Week 8, and  $\pm 5$  days for Weeks 44 and 52.

Patient reported outcomes (PRO) i.e. PHQ-8, and eC-SSRS should be performed before any other study procedures, assessments or consultations.

IGA, BSA and PASI should be conducted after the PROs and before other tests, procedures and consultations.

Study drug should be administered **after** completion of all other study procedures.

The following assessments will be performed and information collected:

- PHQ-8
- eC-SSRS
- IGA
- BSA
- PASI
- AEs - SAEs and AEs will be followed until resolution, stabilization or the event is otherwise explained or the subject is lost to follow up (see Section 7.3). AEs not considered serious or as an AESI will be considered ongoing if they have not resolved by Week 52.
- Concomitant Medications
- Skin Evaluation
- Vital Signs
- Laboratory Analysis Chemistry and Haematology (Central Laboratory)
- Urine Pregnancy Test (Local) – if positive, study drug must be withheld and a Serum Pregnancy Test (Central Laboratory) performed
- Blood Sample for Immunogenicity (must be pre-dose) – subjects testing positive at Week 52 may be requested to provide another sample 6 to 12 months after study completion
- Blood Sample for Pharmacokinetics (must be pre-dose)
- Study Treatment (allocated via IRT) with the exception of Week 52

- At Week 52, male and female subjects of child bearing potential should be reminded that they must use highly effective contraception for a further 4 weeks

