#### **8.1.11 Early Discontinuation**

The Early Discontinuation Visit involves two contacts with the subjects. The subject should attend the study site as close to possible to 4 weeks (28 days) after the last dose of study drug, and prior to the initiation of any other biological therapy. The reason for discontinuation should be discussed with the Medical Monitor. All subjects should then have further follow up either by telephone, or if they have ongoing SAEs or AEs, by attending the study site approximately 8 weeks (56 days) after the last dose of study drug to report any new, and follow up any existing AEs.

Patient reported outcomes (PRO) i.e. DLQI, EQ-PSO, SF-36, PHQ-8, and eC-SSRS should be performed before any other study procedures, assessments or consultations.

IGA, BSA and PASI should be conducted after the PROs and before other tests, procedures and consultations.

The following assessments will be performed and information collected:-

Visit 1 – As close as possible to 4 weeks (28 days) after the last dose of study drug, and prior to the initiation of any other biological therapy.

- DLQI
- EQ-PSO
- SF-36
- PHQ-8
- eC-SSRS
- IGA
- BSA
- PASI
- AEs
- Concomitant Medications
- Skin Evaluation
- Physical Examination
- Vital Signs
- Laboratory Analysis Chemistry and Haematology (Central Laboratory)
- Urinalysis (Local)
- Urine Pregnancy Test (Local)
- ECG (Standard 12 Lead, Central ECG Laboratory)
- Blood Sample for Immunogenicity – subjects testing positive may be requested to provide another sample six to twelve months after study completion
- Blood Sample for Pharmacokinetics

Visit 2 / Telephone Call – As close as possible to 8 weeks (56 days) after the last dose of study drug

- AEs
- Concomitant medication
- Male and female subjects of child bearing potential should be reminded that they must use highly effective contraception for a further 4 weeks

Following completion of the Early Discontinuation visits, subjects will continue to be contacted by telephone q4w as per the study schedule up to Week 52. The following information will be collected.

- AEs
- Concomitant medication
- Any new treatments for psoriasis

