### **8.5.1 Time Period and Frequency for Collecting AE and SAE Information**

AEs will be collected from the signing of the informed consent form (ICF).

Medical conditions that begin before the start of study drug but after obtaining informed consent will be recorded on the Medical History/Current Medical Conditions section of the eCRF, not the AE section, unless related to study procedures.

All SAEs will be recorded and reported to the sponsor or designee within 24 hours, as indicated in Section 10.3, Appendix 3. The investigator will submit any updated SAE data to the sponsor within 24 hours of it being available.

Investigators are not obligated to actively seek AE or SAE information after the conclusion of a subject's study participation. However, if the investigator learns of any SAE, including a death, at any time after a subject has been discharged from the study, and he/she considers the event to be reasonably related to the study drug or study participation, the investigator must promptly notify the sponsor.

The method of recording, evaluating, and assessing causality of AE and SAE and the procedures for completing and transmitting SAE reports are provided in Section 10.3, Appendix 3.

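### For completers, the visit windows let the last scheduled AE enquiry fall 46 to 66 days after the last dose, so the schedule alone does not deliver the stated 8 weeks

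*Protocol*

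**What the plan says.** Protocol 8.5.4 sets a minimum: "AEs/SAEs must be followed up and reported as appropriate for at least 8 weeks (5 terminal half lives) after the last study dose". SAP 1.4 states the same 56 days for all subjects, whether they complete or discontinue. SAP 4.9.2.5 runs the overall treatment-emergent window to 8 weeks after the last dose.

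For completers, Protocol 6.7 fixes the two dates that matter: "The final dose of study drug will be administered at the Week 44 visit with the final study visit occurring at Week 52". The Schedule of Activities (1.3) puts these at Days 309 and 365. Protocol 8.1.6 and the Schedule of Activities allow ±5 "days for Weeks 44 and 52". Protocol 8.0 gives the anchor: "Study visit dates are scheduled relative to Week 0".

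Subjects who stop treatment early have a second safety contact tied to their own last dose: "As close as possible to 8 weeks (56 days) after the last dose of study drug" (8.1.11). No equivalent contact is listed for completers. Under 4.4, the "end of study participation for each subject will be after 52 weeks", and 8.5.1 adds: "Investigators are not obligated to actively seek AE or SAE information after the conclusion" of participation.

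**The concern.** The 8-week figure is written as a floor, but the completer schedule only aims at it. The planned gap has no slack, each end can move by 5 days, and a late Week 44 dose does not move the Week 52 visit. A site can therefore keep every visit window and still ask its last AE question before day 56.

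What is at stake is detection of new events late in the washout. Events already known are covered. Under 8.5.3, "SAEs and AEs will be followed until resolution, stabilization, the event is otherwise explained, or the subject is lost to follow-up", although non-serious events that are not of special interest are closed as ongoing at Week 52. Clinically significant laboratory values are repeated (8.4.5), and related SAEs learned of later must be reported (8.5.1). What can be missed is a new event in the last days of the 8 weeks that the subject does not volunteer. The SAP counts those days as treatment-emergent time.

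**Working it through.** **Inputs**
- Last dose: Week 44, Day 309, window ±5 (Protocol 1.3, 6.7, 8.1.6).
- Final visit: Week 52, Day 365, window ±5 (same sections).
- Both timed from Week 0 (Protocol 8.0).
- Required follow-up: at least 8 weeks = 56 days (Protocol 8.5.4; SAP 1.4).
- Terminal half-life: 11 to 12 days (Protocol 2.3).
- Contraception: 12 weeks = 84 days after the last dose (Protocol 5.2, Appendix 4).

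**1. The plan's own figure.** On target days the gap is 365 − 309 = 56 days = 8.0 weeks. Five half-lives are 5 × 11 = 55 to 5 × 12 = 60 days. The stated 8 weeks is therefore reproduced, with no margin.

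**2. The gap with windows.**
- Shortest: (365 − 5) − (309 + 5) = 360 − 314 = 46 days.
- Longest: (365 + 5) − (309 − 5) = 370 − 304 = 66 days.
- Largest shortfall: 56 − 46 = 10 days, or 10/56 = 18% of the period.

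**3. It is not confined to the extremes.** With offsets a (dose) and b (visit) from −5 to +5, the gap is 56 + b − a, which is below 56 whenever b < a. Of the 11 × 11 = 121 in-window pairs, 11 have b = a and half of the other 110 have b < a, so 55 pairs fall short. This counts possibilities and is not a probability. The documents give no data on actual visit timing.

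**4. In half-lives.** For a subject given M1095 at Week 44, 46 days is 46/12 = 3.8 to 46/11 = 4.2 half-lives, against 56/12 = 4.7 to 56/11 = 5.1 at 56 days.

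**5. Is a compliant date always available?** The visit must fall on or after dose day + 56 and no later than Day 370.
- Dose on Day 304: Days 360 to 370 (11 days).
- Dose on Day 309: Days 365 to 370 (6 days).
- Dose on Day 314: Day 370 only (1 day).

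So it always exists, but it can be a single day.

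**6. The contraception reminder.** At Week 52, Protocol 8.1.6 tells subjects to continue for four more weeks. On target dates that gives 56 + 28 = 84 days, as required. At the shortest gap it gives 46 + 28 = 74 days, 10 short.

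**The case against.** The strongest reply is that 8.5.4 is itself in the protocol and binds sites, and that a visit window is a tolerance which waives nothing. Since step 5 shows that both rules can always be met together, a reader who inferred that the two texts contradict each other would go too far. That much stands. It does not remove the point, because no visit, call or window rule puts 8.5.4 into practice for completers. Compliance depends on each site noticing that an in-window visit may be too early.

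It can also be said that 8.5.4 sits under SAE reporting and does not require a question on or after day 56 in so many words. That is fair. But SAP 1.4 states 56 days of safety follow-up for completers, and without a contact, follow-up for new events rests on the subject coming forward.

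Other dose-based duties do outlast an early Week 52 visit. Laboratory abnormalities within eight weeks of the last dose are repeated (8.4.5), and pregnancies are collected to at least 12 weeks (8.5.5). These narrow the gap without covering new AEs in general.

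The discontinuers' contact is itself approximate and has no lower bound, so it does not guarantee 8 weeks either. The difference is only that it moves with the actual last dose.

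Finally, subjects still on dose hold receive placebo at Week 44. Protocol 6.0 counts placebo as study drug, so 8.5.4 applies to them, but a short gap has little pharmacological meaning in that group.

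On contraception, the 12-week rule is stated correctly in 5.2 and Appendix 4, and Appendix 4 words the final reminder as a minimum of four more weeks. Only the reminder needs tidying.

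**Conclusion.** The point holds as a low-end minor one: the completer schedule does not by itself secure the 8 weeks stated in Protocol 8.5.4 and SAP 1.4. The shortfall is at most 10 days in any one subject. It reaches that size only if the last dose is at the late edge of its window and the final visit at the early edge. How often any shortfall would occur cannot be told from the documents.

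Two stronger readings are not supported. A reader might infer from 4.4 that participation, and with it the duty to ask about AEs, stops on Day 365 even when the final visit is still to come. The text says after 52 weeks, and the Schedule of Activities allows the visit up to Day 370, so ending participation before an in-window visit is a strained reading. A reader might also infer a material bias in exposure-adjusted AE rates, because SAP 4.7.1 credits a fixed 56 days after the last dose. At most 10 days per completer lack a scheduled question, and only where the visit comes early, so the effect is negligible. The Week 12 primary analysis is not affected at all.

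**What to change.** In Protocol 1.3 and 8.1.6, make two additions.
- The Week 52 visit should preferably take place at least 56 days after the actual last dose, within the existing window (latest Day 370).
- Any completer seen earlier receives one short AE telephone call on or after day 56.

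The call should be the main safeguard. A hard lower bound on the visit would leave a single permissible day after a Day 314 dose, and would invite deviations at a visit that also carries efficacy, PK and antibody assessments. Moving the Week 52 window to 0/+5 while keeping the Week 0 anchor would not be enough, since 365 − 314 = 51 days would still be allowed.

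In the same edit, have the Week 52 reminder give the calendar date 12 weeks after the actual last dose in place of a fixed four weeks, and align the matching sentence in Appendix 4.

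The cost is a few lines of wording, some scheduling attention at sites, and one short call for each completer seen early. About 60 sites are planned, so the text is best carried in the next amendment. Because the call only carries out what 8.5.4 already requires, a site instruction could start it sooner.

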### **8.5.5 Pregnancy**

Details of all pregnancies in female subjects and female partners of male subjects will be collected after the start of study treatment and until at least 12 weeks (>5 terminal half lives) after the last study dose.

If a pregnancy is reported, the investigator should inform the sponsor within 24 hours of learning of the pregnancy and should follow the procedures outlined in Section 10.4, Appendix 4.

Abnormal pregnancy outcomes (e.g., spontaneous abortion, fetal death, stillbirth, congenital anomalies, ectopic pregnancy) are considered SAEs and should be reported to the sponsor or designee within 24 hours.

### **8.5.6 Cardiovascular and Death Events**

Cardiovascular AEs should be reported as AEs/SAEs as described in Sections 8.5 and 10.3, Appendix 3.

Any subject deaths that occur during the study should be considered SAEs and reported as per Sections 8.5 and 10.3, Appendix 3. If a death occurs, the investigator may be asked to provide a copy of any post-mortem findings including histopathology.

### **8.5.7 Disease-Related Events and/or Disease-Related Outcomes Not Qualifying as AEs or SAEs**

All AEs and outcomes should be reported as described in Sections 8.5 and 10.3, Appendix 3.

## **8.6 Overdose and Medication Errors**

There is no data regarding overdose of M1095.

Secukinumab doses of up to 30 mg/kg intravenously have been administered in clinical trials without dose-limiting toxicity. In the event of overdosage, it is recommended that the subject

be monitored for any signs or symptoms of adverse reactions and appropriate symptomatic treatment be instituted immediately.

Medication errors may result, in this study, from the administration of an unassigned treatment to the wrong subject, errors related to storage requirements, or administration of an expired product. All overdoses occurring to a study subject are to be captured on the AE page of the eCRFs and on the SAE form when appropriate. In the event of medication dosing error, the sponsor should be notified immediately.

Medication errors are reportable irrespective of the presence of an associated AE/SAE, including:

- Medication errors involving subject exposure to the study drug.
- Potential medication errors or uses outside of what is foreseen in the protocol that do or do not involve the participating subject.

Whether or not the medication error is accompanied by an AE, as determined by the investigator, the medication error, and, if applicable, any associated AE(s) is captured on an AE eCRF page.

## 8.7 Pharmacokinetics

Pharmacokinetic samples will be collected at the timepoints specified on the SoA (Section 1.3).

Samples will be shipped initially to the study's central laboratory and tested by the sponsor or sponsor's designee.

Serum M1095 levels will be assessed at trough (i.e. before study drug is given) at the following visits: Weeks 0, 2, 4, 8, 12, 24, 36, 44, 48, 52 and Early Discontinuation. M1095 serum concentrations will be summarized at these timepoints.

Drug concentration information will not be reported to investigative sites or blinded personnel until the study has been unblinded.

Details of the analysis will be provided either in the Statistical Analysis Plan (SAP), or in a separate PK Plan, prior to the analysis taking place.

## 8.8 Pharmacodynamics

Pharmacodynamic parameters are not evaluated in this study.

## 8.9 Genetics

Planned genetic analysis is not performed in this study. Unscheduled genomic biomarkers may be assessed as described in Section 8.10.

## 8.10 Biomarkers

Biomarkers are not routinely evaluated in this study. However, if a subject develops a clinically significant cutaneous rash that is not typical of psoriasis, two  $\geq 4$ mm punch biopsies, one of normal skin, and one from skin within the rash will be obtained. The biopsies will be prepared and sent to a specialist laboratory for analysis of genomic biomarkers, specifically the expression of inflammatory mediators that characterize various immune reactions.

### 8.10.1 Immunogenicity Assessments

Antibodies to M1095 will be evaluated in serum samples collected at the timepoints specified on the SoA (Section 1.3)

Samples will be shipped initially to the study's central laboratory and tested by the sponsor or sponsor's designee.

Serum anti-drug antibodies will be assessed at trough (i.e. before study drug is given) at the following visits: Weeks 0, 2, 4, 8, 12, 24, 36, 44, 48, 52 and Early Discontinuation.

Serum samples will be screened for antibodies binding to M1095 and the titer of confirmed positive samples will be reported. Other analyses may be performed to verify the stability of antibodies to M1095 and/or further characterize the immunogenicity of M1095.

The detection and characterization of antibodies to M1095 will be performed using a validated assay method by or under the supervision of the sponsor. All samples collected for detection of antibodies to study drug will also be evaluated for M1095 serum concentration (see Section 8.7) to enable interpretation of the antibody data. Positive samples for anti-drug antibodies will be evaluated to determine if the antibodies are neutralizing or non-neutralizing.

If a subject's final anti-drug antibody sample is positive (i.e. sample from Week 52 or sample from an Early Discontinuation visit) then the sponsor may request an additional sample be collected approximately six to twelve months after completion of the study. Subjects will be informed of this in the consent form and will have the option to refuse this additional sample.

With a subject's consent, samples may be stored following the last subject's last visit for the study at a facility selected by the sponsor to enable further analysis of immune responses to M1095.

